7.2.2. Planned CV Safety (MACE) Co-Primary Statistical Analyses

CV Safety (MACE) Co-Primary Statistical Analyses
Endpoint(s)

 • Time to first occurrence of adjudicated MACE • The Cox Proportional Hazards model will adjust for the following baseline categorical values: 
 ○ Treatment ○ Current ESA use (as randomized, see Section 10.10.2) ○ Region (as randomized, see Section 10.9 & Section 10.10.2) • Confidence intervals for the rate per 100 person-years will also be reported. For within-group rates, the two-sided 95% CI will be obtained using an exact Poisson method. For difference in rates between treatments, the two-sided 95% CI will be constructed with a Normal approximation using Wald’s method [Liu, 2006]. • The co-primary analysis will use only adjudicated safety endpoints as determined by the clinical endpoint committee (CEC) within the time period for follow-up of CV endpoints defined in Section 10.6.4. • Calculation of time-to-event or censoring is described in further detail in Section 10.6.4. • First occurrence of adjudicated MACE for a subject is defined as the first adjudicated event, determined by the event date, that is indicated as all-cause mortality, non-fatal MI or non-fatal stroke with further details in Section 10.6.4.
Model Checking & Diagnostics

 • Refer to Appendix 12: Model Checking and Diagnostics for Statistical Analyses.
Model Results Presentation

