
 • COVID-19 MACE are identified by the CEC through one of the following statements: 
 ○ Definitive death due to COVID-19 ○ Possible death due to COVID-19 ○ Definite COVID-19 related hospitalization (for MIs and strokes) ○ Possible COVID-19 related hospitalization (for MIs and strokes) • A summary of the number and percentage of subjects having first-occurrence adjudicated COVID-19 MACE will be provided by treatment group. The number and percentage of the types of events that make up the first occurrence of adjudicated COVID-19 MACE will also be provided by treatment group. • The additional supportive analysis of MACE excluding adjudicated COVID-19 MACE, will use a structure identical to that described for the co-primary MACE analysis and will exclude those adjudicated COVID-19 MACE. This analysis will use the time period for follow-up of CV endpoints defined in (see Section 10.6.4). • The HR, associated two-sided 95% CI, and one-sided non-inferiority and superiority p-values from this supportive analysis will be included on a forest plot with the co-primary MACE results. • Cumulative first adjudicated MACE hazard ratio and the upper bound of the 95%CI (Dapro vs Darbe) will be estimated using the same Cox Proportional Hazards model specified in the co-primary MACE analysis (See Section 7.2.2). They will be displayed graphically by calendar date, at every half year mark, starting from Jan2018 or later when the Cox Proportional Hazards model could converge. At each half year mark, subjects who have not had their first MACE will be censored at the date of the half year mark. The graph will also show the cumulative number of first adjudicated MACE by calendar date. A vertical reference line will be used to represent the date the pandemic measures begin in the majority of the countries.
Supportive Expanded Covariate Adjusted Analysis

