
 • Date of withdrawal for subjects withdrawing (i.e., subjects who actively withdraw or are deemed lost to follow-up) from study or date of completion of study for subjects who complete the study. If the date of study withdrawal entered in the eCRF is before the last study contact date, the last study contact date will be used as the study withdrawal date for analysis. 
 • Note: Subjects who die while on study are considered as having completed the study • The eCRF allows for the possibility of missing or partial dates to be recorded for the study completion/withdrawal date on the Study Conclusion form (i.e., missing day, or day and month, or day and month and year). In such a case, or in case of subjects who are missing a Study Conclusion form, the following conventions will be applied in order to impute a study completion/withdrawal date: 
 • Missing day: 
 ▪ The last day of the month will be used, unless the last study contact date also occurs in the same month; in the case, the last study contact date will be used. • Missing day and month: 
 ▪ '31' will be used for the day and 'Dec' will be used for the month, unless the last study contact date also occurs in the same year; in this case, the last study contact date will be used. • Missing day, month and year: 
 ▪ The last study contact date will be used. • If both death and study completion/withdrawal have missing or partial dates, they will be imputed as specified (see Section 10.6.1 and Section 10.6.4). If the imputed death date is prior to the imputed study completion/withdrawal date, then the study completion/withdrawal date will use the imputed death date instead.
Planned/Actual Visit Dates

 • Planned/actual visit dates will be defined as follows: 
 ○ Week 28 date: Non-missing Week 28 visit start date (from SV domain), otherwise randomization date + 28*7 ○ Week 36 date: Non-missing Week 36 visit end date (from SV domain), otherwise randomization date + 36*7 ○ Week 52 date: Non-missing Week 52 visit end date (from SV domain), otherwise randomization date + 52*7 ○ End of Study date: Non-missing End of Study visit start date (from SV domain), otherwise the middle of the End of Study window.
Stabilization Period

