Non-CV mortality	Any Non-Cardiovascular primary cause of death
Unknown (sub-category of All-cause mortality)	Any Unknown primary cause of death

Events with an adjudication record, but without an investigator reported record, will also be included in the concordance summaries.

All-cause Hospitalization and All-cause Hospital Re-admission within 30 days

- All-cause hospitalization events are defined to be hospital admissions recorded on the Hospitalization eCRF form with a hospitalization duration ≥ 24 hours.
- All-cause hospital re-admissions within 30 days are defined to be hospital admissions recorded on the Hospitalization eCRF form with a hospitalization duration of ≥ 24 hours and an admission date within 30 days following a previous discharge date of an all-cause hospitalization event, where the previous hospitalization should be \geq as stated above.
- Hospitalization rate (per year) across the study = number of all-cause hospitalization events / [follow-up time (days) / 365.25].
- All-cause hospital re-admission rate (per year) across the study = number of all-cause hospital re-admissions / [follow-up time (days) / 365.25].

CV Safety Endpoints
General Definitions

 • Time to event (days) = date of event – randomization date +1 • Censored time (days) = censoring date – randomization date + 1 • First event person years = (cumulative total time to first event for subjects who have the event + cumulative total of censoring time for subjects without the event) / 365.25 • First event incidence rate (per 100 person years) = (100 * number of subjects with at least 1 event) / first event person years • First event absolute rate difference (per 100 person years) = daprodustat incidence rate (per 100 person years) – darbepoetin alfa incidence rate (per 100 person years)
Evaluation Time Periods for CV Endpoints
Time Period for Follow-up of Cardiovascular Endpoints

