
The period for capturing CV safety endpoints begins at randomization. The end of this time period is the date of study completion/withdrawal, with the exception that if a death has been reported in the clinical database after this time, then the death will be included in the analysis.
 
Any endpoints that occurred before the start of this time period are considered to be prior to the time period for follow-up of cardiovascular safety events, and any endpoints that occurred after the end of this time period are considered to be post the time period for follow-up of cardiovascular safety endpoints.

Time Period for Vital Status

The period for capturing vital status begins at the date of randomization. The end of this time period is defined as follows:
 
 • For all subjects known to have died, use the date of death • For all subjects who complete the study, use the study completion date (see Section 10.6.1) • For all subjects who withdraw from the study, but vital status has been ascertained, and are known to have not died – use the latest date last known to be alive. If vital status has not been ascertained following study withdrawal, use the study withdrawal date. 
Any endpoints that occurred before the start of this time period are considered to be prior to the time period for vital status, and any endpoints that occurred after the end of this time period are considered to be post the time period for vital status.

Time Period for On-treatment Cardiovascular Endpoints

The period for capturing on-treatment CV safety endpoint events begins at the treatment start date. The end of this time period is defined as follows:
 
 • For subjects whose last non-zero dose date is missing and who took randomized treatment, use date of study withdrawal/completion • For subjects continuing on study past the last non-zero dose date +28 days, use (last non-zero dose date + 28) • For subjects whose study withdrawal/completion date is on or before (last non-zero dose date +28), use date of study withdrawal/completion 
If the censoring date as defined above for on-treatment CV safety endpoints is after the censoring date as defined for the primary analysis during the time period for follow-up of CV safety endpoints,

CV Safety Endpoints

then use the censoring date for the primary analysis time period.

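### The COVID-19 calendar-time MACE figure censors every event-free subject at the half-year mark, with no provision for earlier withdrawal or completion, so read literally it departs from the co-primary follow-up rule

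*SAP*

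**What the plan says.** Among the COVID-19 supportive analyses, SAP Section 7.2.2 plans a graph of the cumulative first-MACE hazard ratio and its upper 95% bound at half-yearly calendar dates. A vertical line marks the start of pandemic measures. The hazard ratio "will be estimated using the same Cox Proportional Hazards model specified in the co-primary MACE analysis (See Section 7.2.2"). The censoring date is then given separately: "At each half year mark, subjects who have not had their first MACE will be censored at the date of the half year mark".

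For the co-primary analysis, the same section says: "Calculation of time-to-event or censoring is described in further detail in Section 10.6.4". Section 10.6.4.1 defines the follow-up period for CV endpoints: "The end of this time period is the date of study completion/withdrawal, with the exception that if a death has been reported" later, that death is counted. The withdrawal date itself is set in Section 10.6.1 ("Date of withdrawal for subjects withdrawing", including those deemed lost to follow-up).

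The supportive analysis just before this one, which excludes COVID-19 MACE, invokes the co-primary period by name: "This analysis will use the time period for follow-up of CV endpoints defined in (see Section 10.6.4". The while-on-treatment and expanded-covariate analyses also name their period in Section 10.6.4. The half-year figure does not.

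**The concern.** The figure borrows the co-primary model but states its own censoring date, and that date applies to every subject without a MACE. A subject who withdrew event-free in early 2018 would be counted as at risk and event-free at each later mark, although non-fatal MI and stroke were no longer being collected. Elsewhere in Section 7.2.2, assuming no events after dropout is one extreme of the MACE tipping-point analysis. Here it would be the unlabelled default.

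The stake is how the figure is read. It is there to show whether the hazard ratio and its upper bound moved over calendar time. If the arms differ in withdrawal, the added event-free time moves the curve with no change in treatment effect. Marks after a subject's completion add time in the same way, so the last point need not agree with the co-primary result.

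**Working it through.** **1. The two rules for one subject.** Take a subject who withdraws event-free before a mark and is not later reported dead.
- Co-primary rule: censored at withdrawal (Section 10.6.4.1).
- Half-year rule as written: censored at the mark.
- With "Censored time (days) = censoring date – randomization date + 1", the half-year rule adds (mark − withdrawal date) days of event-free time, and more at each later mark.
- By the same formula, a subject randomized after the mark has zero or negative time. Software would probably drop the record, but the sentence does not say who is included.

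**2. Size: inputs.** The SAP gives no MACE rate, withdrawal rate or accrual length, so there is no figure of its own to reproduce. Assumed: MACE 6.7 per 100 person-years in both arms (true ratio 1), uniform accrual over 2.5 years, mark at 4.2 years, exponential withdrawal unrelated to risk, and no event seen after withdrawal.

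**3. Formulas.** Let λ be the MACE rate, w the withdrawal rate, k = λ + w, and C the time from randomization to the mark (uniform from 1.7 to 4.2 years).
- Probability of an observed event: P = (λ/k)(1 − e^(−kC))
- Person-time, co-primary rule: (1 − e^(−kC))/k
- Person-time, half-year rule: λ[1 − e^(−kC)(1 + kC)]/k² + C(1 − P)

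Average each over C, then divide events by person-time. The co-primary rule returns 6.70 whatever w is.

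**4. Results at 4.2 years.**

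| Withdrawal per year | Half-year-rule rate per 100 PY |
|---|---|
| 4% | 6.287 |
| 6% | 6.095 |

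- 4% in both arms: each rate is understated by 1 − 6.287/6.70 = 6%, but the ratio is unbiased.
- 6% on daprodustat, 4% on darbepoetin alfa: 6.095/6.287 = 0.969. A simulation with 500,000 per arm gives (6.09/6.69)/(6.30/6.71) = 0.970.
- Arms swapped: 6.287/6.095 = 1.032.
- 5% versus 3%: also about 0.969.

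**5. Cox fit under other assumptions** (control rate 10 per 100 PY, 3-year accrual, mark at year 4, 400,000 subjects):

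| Withdrawal per year, control / daprodustat | HR, co-primary rule | HR, half-year rule |
|---|---|---|
| 3% / 3% | 1.002 | 1.002 |
| 3% / 5% | 0.997 | 0.968 |
| 2% / 6% | 0.992 | 0.938 |
| 6% / 2% | 0.997 | 1.056 |

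Censoring at the earlier of withdrawal and mark, as in the middle column, stays at the true value of 1 within simulation error.

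**6. Shape over calendar time.** For 6% versus 4%, the factor from step 3 at marks of 1.2, 1.7, 2.2, 2.7, 3.2, 3.7 and 4.2 years is 0.992, 0.989, 0.986, 0.982, 0.978, 0.974 and 0.969. The decline is 0.3 to 0.5 percentage points per half-year, with no break.

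**7. Scale.** At the planned 664 events with 1:1 allocation, the standard error of the log hazard ratio is about 2/√664 = 0.078. A 3% shift is |ln 0.970|/0.078 ≈ 0.39 standard errors. The largest hazard ratio meeting the 1.25 margin would be 1.25 × e^(−1.96 × 0.0776) ≈ 1.07.

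**The case against.** The strongest reply is that the half-year mark is only a data cut laid over the usual rules. The bullet cites the co-primary model, and the section it cites sends censoring to Section 10.6.4. The companion haemoglobin display in Section 7.1.2.5 is plainly a data cut, using values available up to each time point. On that reading a subject already censored at withdrawal stays censored there. This is plausible and may be what was meant. It does not settle the matter: the sentence gives a specific censoring date for all event-free subjects, and the neighbouring MACE analyses name Section 10.6.4 where this one does not. A programmer following the text would not apply the earlier date.

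Other parts of the reply stand in full:
- The graph shows the hazard ratio, its upper bound and event counts, not rates, so the 6% understatement of rates would not appear in it.
- Bias in the hazard ratio needs unequal withdrawal, the rates used here are assumed, and the direction reverses if the arms are swapped.
- Deaths reported after withdrawal still count and all-cause mortality is a MACE component, so about 3% is nearer an upper figure for those assumed rates.

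A reader might infer that the rule would mimic a pandemic effect at the reference line. It would not: the drift is smooth and is present before the line as well. A reader might also infer that the curve cannot end at the co-primary hazard ratio. The documents support only that it need not, since with equal withdrawal the hazard ratio is essentially unchanged.

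**Conclusion.** The point holds as a defect in the stated censoring rule of one supportive graph. Followed literally, the rule adds unobserved event-free time and departs from the co-primary follow-up period. The hazard ratio is affected only if withdrawal differs between arms: about 3% in favour of the arm with more withdrawal at an assumed 6% versus 4% per year, less once later-reported deaths are counted, and increasing gradually with calendar time. The figure carries no test or decision rule. The co-primary non-inferiority test, the analysis excluding COVID-19 MACE and the tipping-point analysis are unaffected, and nothing here supports a claim that the MACE conclusion is biased.

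**What to change.** Replace the censoring sentence in the COVID-19 part of Section 7.2.2 with: *At each half year mark, include subjects randomized on or before the mark; subjects without a first MACE by the mark are censored at the earlier of the mark and their co-primary censoring date (Section 10.6.4.1).*

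A subject whose first MACE falls after the mark has no co-primary censoring date. For that subject, use the study completion or withdrawal date in the comparison.

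The cost is one sentence in the SAP and a minimum of two dates in the program. A last point taken at or after study end then equals the co-primary hazard ratio, which also gives a check on the programming.

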8. OTHER STATISTICAL ANALYSES

8.1. Efficacy Analyses

8.1.1. Additional Secondary Efficacy Analyses

8.1.1.1. Overview of Planned Additional Secondary Efficacy Analyses

Table 5 provides an overview of the planned additional secondary efficacy analyses.

Table 5 Overview of Planned Additional Secondary Efficacy Analyses

Endpoint	Analysis Population	Absolute						Change from Baseline							
		Stats Analysis			Summary		Individual		Stats Analysis			Summary		Individual	
		T	F	L	T	F	F	L	T	F	L	T	F	F	L
Hgb Variability															
Hgb change from baseline to Week 52 ^{1,2}	ITT									Y	Y		Y		
Hgb change from baseline to Week 52 by subgroup ^{1,2,3}	ITT									Y	Y				
Hgb responders ²	ITT	Y			Y										
Hgb responders by subgroup ^{2,3}	ITT	Y	Y												
% of time Hgb in analysis range ²	ITT	Y			Y										
% of time Hgb in analysis range by subgroup ^{2,3}	ITT	Y	Y												
Time to Rescue															
Time to stopping randomized treatment due to meeting rescue criteria	ITT	Y	Y		Y										

NOTES:

- T = Table, F = Figure, L = Listing, Y = Yes display generated.
- Stats Analysis = Represents TFL related to any formal statistical analyses (i.e. modelling) conducted.
- Summary = Represents TFL related to any summaries (i.e. descriptive statistics) of the observed raw data.
- Individual = Represents FL related to any displays of individual subject observed raw data.

^[1] Analysis will be performed using all available (on and off-treatment) Hgb values.

^[2] Analysis will be performed using evaluable Hgb values only (see Section 10.6.3).

^[3] Subgroup analysis will only use the region subgroups defined in Section 10.10.1.

8.1.1.2. Planned Secondary Efficacy Statistical Analyses

Hgb Variability

Secondary Efficacy Statistical Analyses: Hgb Variability
Endpoint(s)

 • Hgb change from baseline to Week 52 • N (%) responders, defined as mean Hgb within the Hgb analysis range 10-11.5 g/dL during EP • % time Hgb in analysis range (10-11.5 g/dL) during the evaluation period (EP, Week 28 to 52) and during the maintenance period (MP; Week 28 to end of trial) (non-inferiority analysis that will use a margin of 15 percentage points less time in range)
Model Specification

 • For the secondary analysis of Hgb change from baseline to Week 52, a mixed model repeated measures (MMRM) approach will be used with an unstructured covariance matrix to compare the difference in means between arms. The model will be fitted to Hgb data collected after baseline up to Week 52, excluding values collected during the stabilization period (Randomization date + 1 day to <Week 28). The model will include factors for treatment, time, prognostic randomization stratification factors (as randomized, see Section 10.10.2), baseline Hgb and the baseline Hgb by time and treatment by time interaction terms. Analyses will be done with the MIXED procedure in SAS, using the Kenward-Roger option to estimate denominator degrees of freedom and standard errors. This analysis will be performed using all available Hgb values (on and off-treatment) and separately using evaluable Hgb values only (see Section 10.6.3). In the analysis using all available Hgb values, subjects who withdraw from the study before Week 52 are considered to be missing at random and in the analysis using evaluable Hgb values, subjects who permanently discontinue randomized treatment before Week 52 are assumed to be missing at random. • For the Hgb responder analysis, mean Hgb during the EP will be defined as in the while on-treatment supportive analysis (Section 10.6.3). Responders will be subjects with a mean Hgb during the EP that falls within the Hgb analysis range of 10-11.5 g/dL. A Cochran-Mantel-Haenszel (CMH) chi-squared test, adjusting for treatment and the prognostic randomization stratification factors (as randomized, see Section 10.10.2), will be used to compare the number and % of responders between the treatment groups. • For the analysis of % time in range, the method by Rosendaal [Rosendaal, 1993] will be used to calculate the percentage of time (days) a subject's Hgb is below, within and above the Hgb analysis range of 10 to 11.5 g/dL during the EP (Weeks 28-52) and separately during the MP (Week 28 – end of study) (See Section 10.6.3). A van Elteren test (stratified Wilcoxon rank sum test) will be used to compare the percentage of time in range between treatment arms, adjusting for treatment and the prognostic randomization stratification factors (see Section 10.10.2). This analysis will be performed using evaluable Hgb values only. Hodges-Lehmann

Secondary Efficacy Statistical Analyses: Hgb Variability
estimate of the treatment difference will be used to assess non-inferiority in % time in range.
Model Results Presentation

 For the MMRM analysis of change from baseline in Hgb, an LSMEANS statement will provide adjusted treatment group means and standard errors and a point estimate and two-sided 95% confidence interval for the adjusted mean treatment difference (daprodustat – darbepoetin alfa) at Week 52. The one-sided non-inferiority p-value for this test will be calculated. For the responder analysis, the number and percentage of subjects with mean EP Hgb, mean MP Hgb, and end of treatment Hgb above, within and below the Hgb analysis range will be summarized by treatment group. For the responder analysis, the number and % of responders by treatment group, difference in response rate (daprodustat – darbepoetin alfa) and two-sided 95% CI using Wald method will be provided along with the one-sided CMH p-value for the treatment group comparison. If the CMH adjusted treatment difference is positive, then the one-sided p-value is p/2, and if the CMH adjusted treatment difference is negative, then the one-sided p-value is 1-p/2, where p is the two-sided p-value from the CMH test. The % time Hgb is above, in and below the Hgb analysis range (10-11.5 g/dL) during the MP and the EP will be summarized using mean, standard deviation, minimum, P25, median, P75, and maximum by treatment group. The percent time in range for each treatment group, the stratified Mann-Whitey estimate of the treatment difference (daprodustat – darbepoetin alfa) and associated two-sided 95% CI [Kawaguchi, 2011] will be presented in addition to the one-sided superiority p-value from the van Elteren test. Hodges-Lehmann estimate of the treatment difference (daprodustat-darbepoetin alfa) and associated two-sided 95% CI will be presented.
Model Results Interpretation

 For the MMRM analysis of change from baseline in Hgb, the NI margin used in the co-primary analysis of Hgb (-0.75 g/dL) will be used for reference in this comparison, thus generating support for non-inferiority if the lower bound of the two-sided 95% CI is above -0.75 g/dL. For the responder analysis, the one-sided CMH p-value will be compared to 0.025 to assess nominal significance. For the percent time in range analysis, a NI margin of -15% will be used as a reference in this comparison, thus generating support for non-inferiority if the lower limit of the two-sided 95% CI of Hodges-Lehmann estimate is above -0.15. If non-inferiority is established, nominal superiority will be achieved if the one-sided p-value is < 0.025.

Supportive Statistical Analyses
Subgroup Analysis

 Subgroup analyses will be performed for the Hgb change from baseline to Week 52 analysis and the Hgb responder during EP analysis, using the region and current ESA use at randomization subgroups only (described in Section 10.9.1 & Section 10.10), in a method similar to that described for the subgroup analyses of the co-primary and principal secondary analyses. Subgroup analyses will be performed for the percent time in range, using the region subgroups only (described in Section 10.9.1 & Section 10.10), in a method similar to that described for the subgroup analyses of the co-primary and principal secondary analyses.

Time to Rescue

Secondary Efficacy Statistical Analyses: Time to Rescue
Endpoint(s)

 Time to stopping randomized treatment due to meeting rescue criteria
Model Specification

 Analysis of the endpoint above will be performed using an analysis model identical to that described for the co-primary MACE analysis. Analysis will include only those efficacy endpoints occurring within the time period for treatment discontinuation. Calculation of time-to-event or censoring is described in further detail in Section 10.6.3. Time to stopping study medication due to meeting rescue criteria is defined as the time from Randomization until the date on which a subject permanently stops study medication due to meeting criteria for rescue.
Model Results Presentation

 Summaries will include (see Section 10.6.3): 
 the number and percentage of subjects meeting evaluation criteria for rescue and the number of occurrences (events), the number and percentage of subjects unable to be evaluated for rescue, and the number and percentage of subjects meeting rescue. The analysis model results presentation will be identical to the co-primary MACE model results, with the following exceptions: 
 The one-sided p-value presented will be for the test of superiority of daprodustat vs. darbepoetin alfa. The forest plot figure will not be created for the time to stopping study medication due to meeting rescue criteria endpoint.
Model Results Interpretation

 One-sided p-values will be compared to 0.025 to assess nominal significance.

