10.10.2. Randomization Stratification

Randomization is stratified by current ESA use, region and by participation in an ABPM sub-study to ensure balance across treatment groups for both the overall parent study and within the ABPM sub-study. The prognostic stratification factors (i.e., current ESA use and region) will be taken into account within the analysis models. Stratification by ABPM sub-study participation was implemented for logistical reasons, and will not be taken into account within analysis models.

Baseline current ESA use strata will be identified by two data sources:

- PPD's IRT dataset
- eCRF

The proposed approach is to use the IRT strata in the adjusted analysis models in order to provide a randomization-based test statistic in accordance with the principle of 'analyze as randomized'. In summaries of subgroups however, the actual status of the factor for stratification derived from the eCRF form will be used.

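### Hgb responder analysis: the displayed difference and Wald interval name no strata, while the CMH p-value beside them is stratified by ESA use and region

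*SAP*

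**What the plan says.** SAP Section 8.1.1.2 (Hgb Variability) defines the endpoint: "Responders will be subjects with a mean Hgb during the EP that falls within the Hgb analysis range of 10-11.5 g/dL". The test is a CMH chi-squared test which, "adjusting for treatment and the prognostic randomization stratification factors (as randomized, see Section 10.10.2), will be used to compare the number and % of responders" between arms.

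For presentation, the same section lists the number and percentage of responders by arm, and then the difference in response rate, daprodustat minus darbepoetin alfa, for which a "two-sided 95% CI using Wald method will be provided along with the one-sided CMH p-value". The direction of that p-value comes from another quantity: "If the CMH adjusted treatment difference is positive, then the one-sided p-value is p/2", and one minus p/2 if it is negative. That adjusted difference is not among the items to be displayed.

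Interpretation rests on the test only: "For the responder analysis, the one-sided CMH p-value will be compared to 0.025 to assess nominal significance". Section 10.10.2 gives the general rule: "The prognostic stratification factors (i.e., current ESA use and region) will be taken into account within the analysis models", using the strata held in the randomization system. Section 2.2 lists the endpoint as secondary, without multiplicity adjustment.

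**The concern.** The plan appears to hold two treatment differences. One is displayed with an interval and no stated adjustment. The other is adjusted for the strata, sets the sign of the p-value and is not shown. A reader of the results table then has no effect estimate that corresponds to the p-value beside it.

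It also departs from how the SAP treats the other two endpoints in the same table. Hgb change to Week 52 gets a model-adjusted mean difference with its CI. Percent time in range gets a stratified Mann-Whitney estimate with its CI beside the stratified van Elteren test. Only the responder endpoint has a stratified test with no stratified estimate.

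If response differs between strata, a crude interval carries between-stratum variance that stratified randomization has already balanced out. It is then wider than necessary and can include zero while the CMH p-value is below 0.025.

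**Working it through.** The SAP gives no response rate, power or between-stratum spread for this endpoint, so there is no figure to reproduce. Two checks were made.

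**1. Standard error by formula.** The total binary variance is p(1−p). It equals the average within-stratum variance plus s², where s is the between-stratum SD of the response rate. Hence

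crude SE / stratified SE = √[ p(1−p) / (p(1−p) − s²) ].

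With p = 0.65 (assumed), p(1−p) = 0.65 × 0.35 = 0.2275.

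| s (assumed) | p(1−p) − s² | stratified/crude SE | crude/stratified SE | crude SE too large by |
|---|---|---|---|---|
| 0.05 | 0.2250 | 0.994 | 1.006 | 0.6% |
| 0.10 | 0.2175 | 0.978 | 1.023 | 2.3% |
| 0.15 | 0.2050 | 0.949 | 1.053 | 5.3% |

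**2. Agreement of interval and test by simulation.** There were 20,000 trials per scenario.

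- From the SAP: N = 4500 and 1:1 allocation (Section 2.3); 5 regions × 2 ESA-use levels = 10 strata (Sections 10.9.1 and 10.10.2).
- Assumed: 75% evaluable in each arm (4500 × 0.75 / 2 ≈ 1,690 per arm), control response 60% or 70%, stratum shares, spread of stratum rates, and a true difference of 0 or 3.5 points.

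Three analyses were compared: crude difference with Wald CI, 10-stratum CMH test, and Mantel-Haenszel difference with stratified Wald CI. Results at a true difference of 3.5 points:

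| Spread of stratum rates | Crude/stratified SE | Crude Wald CI and CMH decision disagree |
|---|---|---|
| none | 1.002 | 0.8–0.9% |
| ±10 points | 1.011–1.013 | 2.0–2.4% |
| ±20 points | 1.039–1.046 | 4.8–5.5% |
| ±28 points | 1.079–1.086 | 7.4–8.6% |

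In the scenario with 70% response and ±28 points, the realised mean difference was 3.2 points. At the widest spread most disagreements were a CMH p-value below 0.025 with a Wald CI that includes zero (6.4–7.6% of trials, against 1.0% the other way).

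Under no true difference:

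- The two disagreed in 0.2–1.1% of trials.
- With heterogeneous strata, the crude and adjusted differences had opposite signs in 2–7% of trials.

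In every scenario the mean crude and mean Mantel-Haenszel differences agreed to within 0.01 percentage points. With the Mantel-Haenszel difference and its stratified CI, disagreement with CMH was 0.2–0.3% at 3.5 points and at most 0.07% under no difference.

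**The case against.** The strongest reply is that the analysis that decides is correctly stratified. Nominal significance rests on the CMH p-value alone, and no conclusion is drawn from the Wald interval. A reader might infer that the plan ignores its randomization strata for this endpoint. The SAP does not support that, because the test uses them as randomized. This part of the reply stands in full.

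Second, the SAP never calls the difference or the interval unstratified. Wald names the form of an interval, and a Wald interval can be built around a Mantel-Haenszel difference. This is fair: the crude reading is an inference. It is still the natural one, because no weights are named and the adjusted difference is mentioned separately and left out of the display.

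Third, the SAP uses simple absolute differences elsewhere. The MACE analysis (Section 7.2.2) gives a Wald interval for a rate difference beside a Cox result. The parallel is only partial, since MACE also reports an adjusted hazard ratio with its own CI.

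Fourth, the disagreement rates at 3.5 points are close to a worst case. With about 1,690 per arm, that difference gives z of about 2.1 at 60% response, next to the 1.96 boundary: √[(0.60 × 0.40 + 0.635 × 0.365)/1687.5] = 0.0167, and 0.035/0.0167 = 2.09. The 7–9% figures also need a very wide assumed spread. Both limits stand.

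**Conclusion.** The point holds as a minor mismatch between the displayed estimate and the test. The displayed responder difference and interval carry no stated stratification, and the stratified difference behind the p-value's direction is not reported. Under the assumptions above, the cost is a standard error about 0.6% to 5.3% too large and an occasional disagreement between interval and p-value. For stratum spreads up to ±10 points, that disagreement occurs in about 2% of trials or fewer even near the significance boundary.

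A reader might also infer a biased estimate or an inflated error rate. Neither is supported: stratified 1:1 randomization makes the crude difference nearly unbiased, and its interval errs on the wide side. One limit applies to the simulation, which took the same evaluable fraction in both arms. Responders are defined on evaluable on-treatment Hgb, so stratum balance among those analysed is likely but not guaranteed.

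The endpoint is secondary, its significance is nominal, and it lies outside the Holm family in Section 10.11.1.2. No trial conclusion depends on it.

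**What to change.** In SAP Section 8.1.1.2, replace the displayed difference and Wald interval with the Mantel-Haenszel stratum-weighted risk difference (daprodustat minus darbepoetin alfa) over the 10 ESA-use by region strata from the randomization system. Give its stratified 95% CI and place both beside the CMH p-value. State that this is the adjusted difference that sets the direction of the one-sided p-value. Keep the crude number and percentage of responders by arm as description.

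The cost is about one sentence of SAP wording and a standard software option, with no new data and no change to the test. The small downside is that the crude arm percentages will not subtract exactly to the displayed difference, which a table footnote can explain.
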